5.3. SUBJECT RESPONSIBILITIES

The subject responsibilities are as follows:

- Use the provided AM & PM Cleanser twice daily (morning and evening) to wash your full face for the duration of the study.
- *Regimen 1 subjects only:* Every evening for the duration of the study: after washing and drying your face, use the PM Mask Treatment for 10 minutes.
- *Regimen 2 subjects only:* Every evening for the duration of the study: after washing and drying your face, apply the provided PM Gel-Cream full-face and let it dry prior to using the PM Mask Treatment for 10 minutes (mask treatment should begin within 15 minutes after PM Gel-Cream application).
- Use only the assigned products and your regular, non-medicated (other than SPF, which is acceptable) facial products that you have used for at least one month and that have been recorded/approved by the study staff at Visit 1 (see section 5.4).
- Do not use any other light-based devices or receive any professional or aesthetic facial spa procedures during the study.
- Do not shave or use any hair removal method on your face within the 24 hours prior to a study visit.
- Do not start using any new personal care products (e.g. makeup, lotions, etc.) or change your currently used brands during the study.
- On the day of study visits: remove all leave-on facial products (including eye makeup) and wash with the provided facial cleanser 30 minutes to 2 hours prior to the visit and then do not apply any leave-on facial products until the visit is completed. Note: if you do not follow these directions, you will be asked to remove your makeup/products and wash your face with the provided cleanser on-site and then wait 30 minutes before evaluations are performed.
- Avoid excessive sun/UV exposure (including tanning beds) for the duration of the study.
- Attend all scheduled visits.
- Do not begin any other clinical study during the current study.
- Report any side effects, changes in health/medication, pregnancies, issues, or questions to the study staff.
- Bring your study products to all visits. Products must be returned at the final study visit. Failure to return your products may result in forfeiture of compensation.

See section 6 regarding detailed product usage instructions.

5.4. CONCURRENT PRODUCTS

During the study, subjects may not use any products on their face other than the assigned IPs and the subject's regular facial products that have been recorded and approved by study staff at Visit 1.

Protocol Title: A Multi-Center, Evaluator Blinded, Randomized Clinical Study to Evaluate the Efficacy and Tolerance of Two Acne

Treatment Regimens on Subjects with Mild to Moderate Acne Vulgaris

Protocol Number: PS-1701 0314 5529-SACT

Date & Version: 06 March 2017, Final Version 1.0

To be approved, the subject's regular facial products (moisturizers, eye makeup removers, color cosmetics, etc.):

- must be recorded by the study staff at Visit 1.
- must have been used for at least one month prior to study start.
- must be non-medicated [other than SPF] and not contain benzoyl peroxide, salicylic acid, alpha hydroxy acids (AHAs), vitamins A (retinol) or C (ascorbic acid) or their analogs or derivatives. The presence of SPF in products is acceptable.
- cannot include cleansers, scrubs, cleansing products, masks, makeup removers/wipes (except to remove eye makeup only), or light-based devices.
- must be maintained over the course of the study. Intermittent recreational sunscreen usage (minimum SPF 30 recommended for face) is allowed if sun exposure is unavoidable.

A subject should not shave or use any hair removal method on his/her face within the 24 hours prior to a study visit. Subjects should not receive any professional or aesthetic facial spa procedures during the study.

For the rest of the body, subjects should not start using any new personal care products (e.g. cleanser, treatments) or change their currently used brands during the study.

5.5. CONCURRENT MEDICATION

If a subject is taking any medication during the course of the study or within 1 month prior to the study, it must be recorded on the Concomitant Medication Form. Minimum information required is the name of the medication.

If this medication is linked to the treatment of a study/IP-related AE, the dose and duration of the treatment should be specified.

Medications/therapies excluded are indicated in the Subject Exclusion criteria; the use of any excluded medications/therapies during the study will result in discontinuation of the subject.

5.6. SCREENING FAILURE

All individuals who signed the ICD/Accent Form and withdraw their participation or fail to meet all of the screening criteria during the initial evaluation will be considered a "screening failure." Data for screen failures will not be considered in the final report.

An individual who is screen-failed but may qualify at a later time may be re-screened at the PI's discretion, but the individual should be treated as a new candidate (i.e. new subject ID, new ICD, etc.). Any individual who screen fails and has an AE will not be re-screened.

Protocol Title: A Multi-Center, Evaluator Blinded, Randomized Clinical Study to Evaluate the Efficacy and Tolerance of Two Acne

Treatment Regimens on Subjects with Mild to Moderate Acne Vulgaris

Protocol Number: PS-1701 0314 5529-SACT

Date & Version: 06 March 2017, Final Version 1.0

6. INVESTIGATIONAL PRODUCTS (IPs)

6.1. IDENTITY OF IPs

The following IPs will be supplied by the Sponsor:

Product Identity (As Labeled)	██████████	Regulatory Classification & Marketing Status	Included in Regimen 1?	Included in Regimen 2?
AM & PM Cleanser ^a	██████████	Cosmetic – Marketed	✓	✓
PM Gel-Cream	██████████	Device – Non-Marketed	---	✓
PM Mask Treatment ^b	██████████	Device – Marketed	✓	✓
Replacement Mask Activator	██████████	Device – Marketed	✓	✓

^aA few additional units of the cleanser will be provided for on-site usage prior to acclimation, as needed.

^b██████████ A Replacement Mask Activator will be supplied to subjects at Baseline (Visit 1), Week 4 (Visit 4), and Week 8 (Visit 5).

The non-marketed IP will be manufactured by the Sponsor or its agents under GMP conditions; the marketed IPs will be commercially sourced. A Letter of Non-Significant Risk will be provided to the PIs for use of the non-marketed device in this study, and the commercial package inserts will be provided to the PIs as reference safety information for the marketed devices. The ingredient list for each of the formulated products is provided in Appendix XIV.

6.2. PACKAGING AND LABELING

The marketed cosmetic product will be used in its original commercial packaging over-labeled under GMP conditions. The marketed devices will be transferred to blinded packaging and the commercial package inserts (containing claims and consumer call center information) will be removed; brand markings on the devices themselves will be over-labeled under GMP conditions.

The study label affixed to each IP unit or packaging may contain (but is not limited to) fields for the following information:

- Protocol Number
- Product Identity (see table in section 6.1)
- Randomization Number (as applicable)
- Directions
- Warnings
- Study Site Identification
- Net Contents or Net Weight
- Site Emergency Contact Information
- Storage Information
- Unit # or Kit # (as applicable)

Protocol Title: A Multi-Center, Evaluator Blinded, Randomized Clinical Study to Evaluate the Efficacy and Tolerance of Two Acne

Treatment Regimens on Subjects with Mild to Moderate Acne Vulgaris

Protocol Number: PS-1701 0314 5529-SACT

Date & Version: 06 March 2017, Final Version 1.0

[REDACTED]

[REDACTED]

[REDACTED]

[REDACTED]

[REDACTED]

Units of the AM & PM Cleanser will also be available for on-site usage prior to acclimation, as needed. Additional PM Mask Treatment units will also be available should a subject need a replacement.

6.3. STORAGE AND ACCOUNTABILITY

The PI or designee must ensure that deliveries of IPs from the Sponsor are correctly received by a responsible person and that the products are stored in a secure area under recommended storage conditions. The products for this study will be secured in a locked room or cabinet that is only accessible to site personnel and kept at 20-25°C (68-77°F) with relative humidity up to 60%. Temperature and relative humidity should be recorded at least daily on business days (an alarm should be utilized to signal if conditions go out of range). The PI or designee must maintain adequate records documenting the receipt, use, loss, or other disposition of the products on the Product Accountability Log or equivalent.

At the end of the study, all IP units (used and/or unused) must be returned to the Sponsor [REDACTED]

[REDACTED]

[REDACTED]

6.4. PRODUCT QUALITY COMPLAINTS

A Product Quality Complaint (PQC) is any written, electronic, or oral communication that alleges deficiencies related to the identity, quality, durability, reliability, or safety of a product, including its labeling, delivery system, or packaging integrity. It also includes device malfunctions. This does not include effectiveness, preference, or performance measures, which will be reviewed in aggregate at appropriate intervals. Any PQC discovered during the initial inventory should follow the instructions provided on the receipt letter; no PQC form should be filed for issues identified when opening or unpacking a shipment. Subsequently, any observation of a PQC requires immediate notification to the Study Manager via a completed PQC form and telephone call. The PI or designee should complete, sign, and forward a copy of the PQC form to the Study Manager listed in Appendix XV.

In addition, PQC information must be included on the Product Accountability Log or equivalent in the comments field. The Study Manager listed can assist you or answer questions related to this process. To aid in the initial conversation and understanding of a PQC, the site staff may be asked to photograph the issue and send it to the Study Manager.

Protocol Title: A Multi-Center, Evaluator Blinded, Randomized Clinical Study to Evaluate the Efficacy and Tolerance of Two Acne

Treatment Regimens on Subjects with Mild to Moderate Acne Vulgaris

Protocol Number: PS-1701 0314 5529-SACT

Date & Version: 06 March 2017, Final Version 1.0

When enrolling subjects into this study, it is the site's responsibility to instruct subjects not to use the product if they have a concern related to the product, labeling, or package integrity and to immediately report it to the study site.

6.5. RANDOMIZATION

Subjects who sign the ICD (or Assent Form, as applicable) will be sequentially assigned a Subject ID. The Subject ID will begin with the four-digit center ID (Academic Dermatology Associates: "1001"; Thomas J. Stephens and Associates, Inc.: "1002") followed by a unique four-digit subject identifier assigned in ascending order and beginning with "1001," resulting in an eight-digit Subject ID (e.g. "10011001," "10011002," etc.). Once a Subject ID has been assigned to a subject, it cannot be reassigned to another subject.

Upon enrollment in the study, each subject will be assigned a unique randomization number, which will determine the treatment assignment for each subject according to a randomization schedule. The randomization scheme will be devised by the Sponsor's Quantitative Sciences Department. For subjects with a score of 2.0 or 2.5 on the IGA assessment, the site will assign randomization numbers in ascending sequential order within the site, i.e. starting with the lowest available number. For subjects with a score of 3.0 or 3.5 on the IGA assessment, the site will assign randomization numbers in descending sequential order, i.e. starting with the highest available number. Once a randomization number has been assigned to a subject, it cannot be reassigned to another subject.

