STATISTICAL METHODS	
The primary efficacy variable is the percent change from baseline in Week 12 global face total lesion count, defined as the sum of inflammatory lesions (papules and pustules), open comedones, and closed comedones.
 
For the primary efficacy variable, treatment means and between-treatment differences will be assessed by means of a one-way Analysis of Covariance (ANCOVA) model with treatment, gender, and center as factors and the corresponding baseline score as a covariate. Monadic efficacy for a treatment will be concluded if the respective mean percent change from baseline is significantly different from zero. Non-inferiority will be concluded if monadic efficacy is demonstrated in both treatments and the upper bound of the two-side 95% confidence interval of treatment difference (mask with topical gel-cream minus the mask alone) is less than 15 percentage points. If non-inferiority is demonstrated, the testing will proceed to superiority test. Superiority of the mask with topical gel-cream treatment will be concluded if the upper bound of the two-sided 95% confidence interval of the treatment difference is less than 0.
 
Each comparison will be tested at the 0.05 significance level, two-sided. With the stepwise procedure, the familywise error rate is controlled at the 0.05 level.

Protocol Title: A Multi-Center, Evaluator Blinded, Randomized Clinical Study to Evaluate the Efficacy and Tolerance of Two Acne

Treatment Regimens on Subjects with Mild to Moderate Acne Vulgaris

Protocol Number: PS-1701 0314 5529-SACT

Date & Version: 06 March 2017, Final Version 1.0

LIST OF ABBREVIATIONS

Abbreviation	Definition
AE	Adverse Event
AHA	Alpha Hydroxy Acid
AIDS	Acquired Immunodeficiency Syndrome
ANCOVA	Analysis of Covariance
CRF	Case Report Form
DPR	Designated Physician Representative
EDC	Electronic Data Capture
EIU	Exposure in Utero
FDA	US Food and Drug Administration
GMP	Good Manufacturing Practices
HIPAA	Health Insurance Portability and Accountability Act
HIV	Human Immunodeficiency Virus
ICD	Informed Consent Document
ICH GCP	International Conference on Harmonisation Good Clinical Practice
ID	Identification
IEC	Independent Ethics Committee
IGA	Investigator Global Acne
IP	Investigational Product(s) (i.e. test products)
IRB	Institutional Review Board
ITT	Intent-to-Treat
LED	Light-Emitting Diode
LOCF	Last Observation Carried Forward
OCMS	Office of Consumer Medical Safety
OTC	Over-the-Counter
PI	Principal Investigator

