8.2.1. Analysis of Primary Variable

The primary efficacy variable is the percent change from baseline in global face total lesion count at Week 12. The total lesion count is the sum of inflammatory lesions (papules and pustules), open comedones, and closed comedones.

The following comparisons will be performed:

1. Mask alone treatment Week 12 vs. baseline
2. Mask with topical gel-cream treatment Week 12 vs. baseline
3. Mask with topical gel-cream treatment vs. mask alone treatment for non-inferiority
4. Mask with topical gel-cream treatment vs. mask alone treatment for superiority

To evaluate the efficacy of the mask alone treatment and the mask with topical gel-cream treatment, statistical comparisons for the primary variable will be based on a stepwise procedure starting with comparisons #1 and #2, which evaluate the monadic efficacy of mask alone treatment and the mask with topical gel-cream treatment, respectively. If both comparisons are significant, testing will proceed to comparison #3 to evaluate the non-inferiority of the mask with topical gel-cream treatment to the mask alone treatment; otherwise, comparison #3 will be exploratory. The difference between treatment groups will be computed as the mask with topical gel-cream treatment minus the mask alone treatment, and non-inferiority will be concluded if the upper bound of the two-side 95% confidence interval is less than 15 percentage points. If the mask with topical gel-cream treatment is demonstrated to be non-inferior to the mask alone treatment, then testing will proceed to comparison #4; otherwise, comparison #4 will be exploratory.

Comparison #4 will evaluate the superiority of the mask with topical gel-cream treatment versus the mask alone treatment. Superiority will be concluded if the upper bound of the two-sided 95% confidence interval of the treatment difference is less than 0.

Each comparison will be tested at the 0.05 significance level, two-sided. With the stepwise procedure, the familywise error rate is controlled at the 0.05 level.

For the primary efficacy variable, treatment means and between-treatment differences will be assessed by means of an Analysis of Covariance (ANCOVA) model with treatment, gender, and center as factors and the corresponding baseline score as a covariate.

If the global face total lesion count is missing at Week 12 for more than 5% of the subjects, the missing value will be imputed by using the last observation carried forward (LOCF) method.

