8.2.2. Analysis of Secondary Variables

The secondary efficacy variables are:

- a) The percent change from baseline in global face total lesion count:
 - Mean across all post-baseline visits (Week 2, Week 4, Week 8, and Week 12)
 - Mean of Week 2 and Week 4
 - Mean of Week 4 and Week 8
 - Mean of Week 8 and Week 12
 - Week 2, Week 4, and Week 8 analyzed separately
- b) Acne lesion counts at Week 2, Week 4, Week 8, and Week 12. Each of the following lesions will be analyzed for the total global face:
 - Open comedones
 - Closed comedones
 - Inflammatory acne lesions (papules and pustules are counted together)
 - Non-inflammatory acne lesions (sum of open comedones and closed comedones)
 - Total lesion counts (sum of inflammatory and non-inflammatory acne lesions counts)
- c) IGA assessment using Modified Cook's Scale at Week 1, Week 2, Week 4, Week 8, and Week 12.
- d) Additional investigator efficacy assessment at Week 1, Week 2, Week 4, Week 8, and Week 12:
 - Overall redness of inflammatory lesions
 - Overall size of inflammatory lesions

For these variables, summary statistics will be summarized by visit and treatment. The mean change from baseline within group and the corresponding 95% confidence interval will be calculated for each variable by treatment and time point. Treatment means and between-treatment differences in change from baseline will be assessed by means of an Analysis of Covariance (ANCOVA) model with treatment, gender, and center as factors and the corresponding baseline score as a covariate. The two-sided 95% confidence interval of the between-treatment difference will be constructed to provide information regarding the extent of the difference between two groups. Percent change from baseline in acne lesion counts will be analyzed using the same methods as for the primary endpoint.

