Appendix III. Investigator Global Acne (IGA) Assessment

The following scale (Modified Cook's Scale) will be used for the IGA assessment.

Half points may be used:

0	Clear	Residual hyperpigmentation and erythema may be present.
1	Almost Clear	A few scattered comedones and a few (less than five) small papules.
2	Mild	Easily recognizable; less than half the face is involved. Many comedones and many papules and pustules.
3	Moderate	More than half of the face is involved. Numerous comedones, papules, and pustules.
4	Severe	Entire face is involved. Covered with comedones, numerous papules and pustules, and few nodules and cysts.
5	Very Severe	Highly inflammatory acne covering the face; with nodules and cysts present.

Protocol Title: A Multi-Center, Evaluator Blinded, Randomized Clinical Study to Evaluate the Efficacy and Tolerance of Two Acne

Treatment Regimens on Subjects with Mild to Moderate Acne Vulgaris

Protocol Number: PS-1701 0314 5529-SACT

Date & Version: 06 March 2017, Final Version 1.0

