6.3. Statistical Methods

6.3.1. Method for Primary Efficacy Endpoint

The mean percent change from baseline in global face total lesion count at Week 12 within the mask with topical gel-cream treatment cell and the mask alone treatment cell will each be tested using a one-sample t-test.

If both of the above comparisons are significant, the non-inferiority of the mask with topical gel-cream treatment to the mask alone treatment will be evaluated; otherwise, this comparison will be exploratory. Treatment means and between-treatment differences will be assessed by means of an ANCOVA model with treatment, gender, and center as factors and the corresponding baseline score as a covariate. The difference between treatment groups will be computed as the mask with topical gel-cream minus the mask alone treatment, and non-inferiority will be concluded if the upper bound of the two-side 95% confidence interval is less than 15 percentage points.

If the mask with topical gel-cream treatment is demonstrated to be non-inferior to the mask alone treatment, the superiority of the mask with topical gel-cream treatment versus the mask alone treatment will be evaluated. Superiority will be concluded if the upper bound of the two-sided 95% confidence interval of the treatment difference is less than 0.

Impact of center on treatment effect will be assessed in a separate analysis by including the center-by-treatment interaction in the ANCOVA model above. Summary statistics will be presented by treatment and center with no statistical comparison between treatments within a center.

If the global face total lesion count is missing at Week 12 for more than 5% of the subjects, the missing value will be imputed by using the last observation carried forward (LOCF) method. In addition, a sensitivity analysis will be performed using a repeated measure mixed model based on the observed data. The model will include the baseline score as the covariate and terms for treatment, gender, center, visit, baseline-by-visit, and treatment-by-visit interactions. The covariance matrix will be assumed unstructured.

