6.3.2. Methods for Secondary and Tertiary Efficacy Endpoints

6.3.2.1. Acne Lesion Counts

Summary statistics of the global face acne lesion counts (open comedones counts, closed comedones counts, inflammatory acne lesion counts, non-inflammatory acne lesion counts, and total lesion counts analyzed separately), change from baseline, and the percent change from baseline (only for inflammatory lesions, non-inflammatory lesions, and total) will be presented by visit and treatment group. The corresponding 95% confidence interval of mean change from baseline and percentage change from baseline will be calculated within treatment group by visit.

Due to the small number (or zero count) of closed comedones and open comedones at baseline, percent change will not be calculated by subject for these two types of lesions. Instead, percent change from baseline in group mean will be presented for each treatment. This will be calculated as post-baseline mean minus baseline mean divided by baseline mean times 100.

The percent (%) of subjects who had improvement in counts and percent (%) of subject who had worsening in counts will also be provided. A reduction of 1 or more lesion from baseline will be considered an improvement. An increase of one or more lesion will be considered a worsening.

Treatment means and between-treatment differences in change from baseline and percent change from baseline will be assessed by means of an ANCOVA model with treatment, gender, and center as factors and the corresponding baseline acne lesion counts as a covariate. The two-sided 95% confidence interval of the between-treatment difference will be constructed.

[figure not shown]

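### Baseline IGA group steers allocation but is absent from the lesion-count, redness and size models; adding it is an optional, low-cost gain in precision

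*Protocol*

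**What the plan says.** Protocol 6.5 gives each site a run of randomization numbers. Subjects with a baseline IGA of 2.0 or 2.5 receive the lowest number still available. At the upper end, "For subjects with a score of 3.0 or 3.5 on the IGA assessment, the site will assign randomization numbers in descending sequential order". Baseline IGA group is therefore used on purpose in allocation within site, although the Protocol does not call it stratification. The section does not say whether the list is blocked.

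The models are described in these places:
- Protocol synopsis, primary variable: "one-way Analysis of Covariance (ANCOVA) model with treatment, gender, and center as factors", plus the baseline score.
- Protocol 8.2.1, primary variable: "model with treatment, gender, and center as factors and the corresponding baseline score as a covariate". SAP 4.5 has the same terms for all primary and secondary variables.
- SAP 6.3.1, primary endpoint: "ANCOVA model with treatment, gender, and center as factors and the corresponding baseline score as a covariate".
- SAP 6.3.1, repeated-measures sensitivity model: "The model will include the baseline score as the covariate and terms for treatment, gender, center, visit, baseline-by-visit, and treatment-by-visit interactions".
- Protocol 8.2.2, secondary variables, including lesion redness and size (item d): "in change from baseline will be assessed by means of an Analysis of Covariance (ANCOVA) model with treatment, gender, and center as factors".
- SAP 6.3.2.1, lesion counts: "ANCOVA model with treatment, gender, and center as factors and the corresponding baseline acne lesion counts as a covariate".
- SAP 6.3.2.3, redness and size: analysed in the same way as the IGA score, so each has its own baseline as covariate.

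Only the ANCOVA of the IGA score itself (SAP 6.3.2.2) adjusts for baseline IGA.

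**The concern.** Allocation uses two groupings, center and IGA group. Center is in every model. IGA group is in none of those listed except the model for IGA itself. Gender is adjusted for although it plays no part in allocation.

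Baseline lesion count, which I take to be the baseline score for the primary endpoint, carries part of what IGA measures. It may not carry all of it, because the scale also grades extent: grade 3 is described as "More than half of the face is involved", and a count does not record that.

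What is at stake is precision:
- **Blocked list.** Drawing from both ends roughly balances the arms within each IGA group. If IGA is prognostic beyond the planned covariates, a model that omits it overstates the standard error slightly and the interval is a little too wide.
- **Unblocked list.** The planned standard error is correct, and the IGA term is ordinary covariate adjustment.

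This bears most on the superiority test, which is planned at only 65% power.

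**Working it through.** **Inputs.** Protocol 8.4 gives 45 completers per arm, SD 30, a margin of 15 points, a true benefit of 5 points for non-inferiority, one-sided 0.025, and a 15-point difference for superiority at two-sided 0.05. The partial R² of IGA group beyond gender, center and baseline value is not in the documents. I assume 0 to 10%.

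**Formulas.** SE = SD × √(2/n). Half-width = t(0.975, df) × SE. Power comes from the non-central t with non-centrality = distance/SE. The distance is 15 + 5 = 20 for non-inferiority and 15 for superiority. With IGA in the model, the residual SD is 30 × √(1 − R²).

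**The plan's own figures.** With 88 df, SE = 30 × √(2/45) = 6.325. Non-inferiority power is 87.9% (stated 87%) and superiority power 65.0% (stated 65%). Both reproduce to within one point.

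**Planned model and model with IGA, 45 per arm.** The planned ANCOVA has five parameters, so df = 90 − 5 = 85; with IGA, df = 84. SD 30 is taken as the residual SD.

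| Model | Residual SD | Non-inferiority power | Superiority power | Half-width |
|---|---|---|---|---|
| Planned | 30.00 | 87.8% | 65.0% | 12.57 |
| IGA, R² 0 | 30.00 | 87.8% | 65.0% | 12.58 |
| IGA, R² 2% | 29.70 | 88.4% | 65.8% | 12.45 |
| IGA, R² 5% | 29.24 | 89.4% | 67.2% | 12.26 |
| IGA, R² 10% | 28.46 | 90.9% | 69.5% | 11.93 |

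**If all 136 are analysed (68 per arm).** The planned SE is 30 × √(2/68) = 5.145. IGA at R² 5% moves non-inferiority power from 97.1% to 97.7%, superiority power from 82.5% to 84.4%, and the half-width from 10.18 to 9.92.

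**If SD 30 is before adjustment.** Protocol 8.4 does not say. If the planned covariates explain an assumed 20%, the residual SD is 30 × √0.8 = 26.83 and the planned model already has 93.8% and 74.6% power. IGA at R² 5% then adds 1.0 and 2.1 points, and the half-width goes from 11.25 to 10.96.

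**Blocked against unblocked list.** This was simulated with 20,000 trials per case: two sites of 45, a 68-number list per site filled from both ends, and IGA groups assumed 50:50. The blocked case assumes blocks of 4.
- *Standard error without IGA, R² 10%.* Blocked: model SE 6.40 against an empirical 6.11, about 5% too large. Unblocked: 6.46 against 6.46.
- *One-sided error at the margin, R² 10%, without then with IGA.* Blocked: 0.0197, 0.0250. Unblocked: 0.0260, 0.0256. The Monte Carlo SE is about 0.0011, so neither case shows inflation.
- *Half-width, unblocked, without then with IGA.* R² 0: 12.83, 12.91. 1%: 12.83, 12.85. 2%: 12.84, 12.79. 5%: 12.83, 12.58. The term begins to help between 1 and 2%.
- *Non-inferiority power if IGA adds nothing.* Blocked: 0.868 with and without. Unblocked: 0.864 falls to 0.862, a loss of 0.2 points. The widening from 12.83 to 12.91 (0.6%) lowers the non-centrality of about 3.10 by 0.019. At a normal density of about 0.215 that is 0.4 points. I take about 0.3.

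**The case against.** The strongest reply is that nothing here is wrong. The covariates are prespecified and the same throughout, the test holds its level, and the power is as stated. That all stands.

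The benefit also rests on two unknowns. IGA is graded largely by lesion quantity, and baseline count is already in the model, so the partial R² may be near the low end. The documents do not show that IGA predicts percent change once count is adjusted for. And the overstated standard error arises only with a blocked list, which is not stated. Both points stand, and they are why the 0 and 2% rows deserve as much weight as the 5 and 10% rows.

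The number analysed may exceed 90. The primary analysis uses the Full Analysis Set, with LOCF when more than 5% of Week 12 counts are missing, and up to 136 may be enrolled. That stands too and reduces the gain.

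A reader might infer something stronger: that allocating by IGA and leaving it out of the model biases the comparison, inflates type I error or invalidates the interval. The documents do not support that. With a blocked list the omission is conservative; with an unblocked list it is neutral.

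None of this removes the case for a cheap prespecified term that uses data already collected. It sets the point's rank as optional.

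**Conclusion.** The point holds as an optional improvement. The plan allocates by IGA group and does not analyse by it, except where IGA is itself the outcome. At an assumed partial R² of 5% with 45 per arm, the term adds about 1.6 points of non-inferiority power (89.4 − 87.8) and 2.2 points of superiority power (67.2 − 65.0), and takes about 0.3 points off the half-width. With 68 per arm the gains are about 0.6 and 1.9 points.

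These figures rest on the assumed R², on SD 30 being the residual SD, and on equal arms. If IGA adds nothing, the loss is about 0 (blocked) to 0.3 points (unblocked) of non-inferiority power.

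**What to change.** Before unblinding:
- Add baseline IGA group (2.0-2.5 vs 3.0-3.5) as a factor to the primary ANCOVA (SAP 6.3.1), the lesion-count ANCOVAs (6.3.2.1) and the redness and size ANCOVAs (6.3.2.3).
- SAP 4.5 covers every primary and secondary variable in one sentence. Reword it to include IGA group and to exempt the IGA ANCOVA (6.3.2.2), which already adjusts for baseline IGA.
- In the repeated-measures model, state that IGA group enters as a main effect.
- Record the change in SAP section 8 as a departure from the Protocol synopsis, 8.2.1 and 8.2.2.

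The cost is this wording and one degree of freedom in each ANCOVA. Baseline IGA is already recorded for every subject as part of eligibility, so no new data are needed. Editing the Protocol instead would mean aligning all three places and an amendment under Protocol 10.1. If the sponsor prefers the current models, one sentence saying why IGA guides allocation but not analysis would close the point.
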